6.4. Planned Analyses and Analyses of Efficacy Analyses that Have Been Conducted

6.4.1. Planned Interim Analyses and Primary Analysis

There were two planned interim analyses in this study, which would be performed when approximately 35% and 70% of the target total number of COVID-19 cases across the two vaccine groups had been observed respectively. The primary objective of the IAs was for early detection of reliable evidence that VE is above 30%. The Lan-DeMets O'Brien-Fleming approximation spending function was used for calculating efficacy bounds and to preserve the (1-sided) 0.025 false positive error rate over the two IAs and the primary analysis (when the target number of cases have been observed), relative to the null hypothesis (H_0^{efficacy} : $VE \leq 30\%$). There is no intention to stop the study early if the efficacy had been demonstrated at any of the IAs. If efficacy was demonstrated at an IA, the subsequent IA or primary analyses would be considered supportive in nature. The IA results would be reviewed by the DSMB.

The first IA would occur when 35% of the total cases in the PP set had been observed. The study would be considered positive at this IA if the one-sided p -value for rejecting $VE \leq$

30% ($HR \geq 0.7$) was less than 0.0002 based on the Lan-DeMets O'Brien-Fleming approximation spending function. This corresponds to an observed HR of approximately 0.259, or an observed VE approximately 0.741.

The second IA would occur when 70% of the total cases have been observed in the PP set. The study will be considered positive at this IA if the p -value for rejecting $VE \leq 30\%$ ($HR \geq 0.7$) was less than 0.0073 based on the Lan-DeMets O'Brien-Fleming approximation spending function. This corresponds to an observed HR of approximately 0.435, or an observed VE of approximately 0.565.

The primary analysis would be performed when approximately 151 cases have been observed in the PP Set. The study would be considered positive at the primary analysis when a total of 151 cases had been observed and if the one-sided p -value for rejecting $HR \geq 0.7$ was less than 0.0227. This corresponds to an observed hazard ratio of approximately 0.505 or observed VE of approximately 0.495.

An independent, unblinded statistics team would carry out the IAs. The unblinded statistics team would not be involved in either study design or the regular study conduct. The subjects and study sites will remain blinded throughout the study.

The final analysis would be performed after all subjects have completed the study and after the database is cleaned and locked. Results of this analysis would be presented in a CSR.

The timing, number of cases and decision guidance at each IA and primary analysis is summarized in the table below (Table 13 of the protocol).

Table 4: Interim Boundaries Using O’Brien-Fleming Spending function, Calculation Based on the PP Set for the Primary Efficacy Endpoint

Information fraction (% of total #cases)	Number of cases	Nominal Alpha	Efficacy Boundary Rejecting H ₀ : VE ≤ 30% (HR ≥ 0.7)	Cum Prob (crossing efficacy boundary if the true VE = 60%)
IA1 35%	53	0.0002	VE ≥ 0.741 (HR ≤ 0.259)	4.6%
IA2 70%	106	0.0073	VE ≥ 0.565 (HR ≤ 0.435)	61.5%
Primary analysis 100%	151	0.0227	VE ≥ 0.495 (HR ≤ 0.505)	90.0%

Abbreviations: HR = hazard ratio; IA: interim analysis; PP = per-protocol; VE = vaccine efficacy.

6.4.2. Analyses of Efficacy that Have been Conducted

Two efficacy analyses have been performed in this study as of this SAP amendment.

6.4.2.1. The First Interim Analysis

The primary efficacy endpoint of mRNA-1273-P301 is COVID-19, defined as the first occurrence of COVID-19 starting 14 days after the 2nd injection.

For the primary efficacy objective, the null hypothesis of this study was that the vaccine efficacy (VE) of mRNA-1273 to prevent first occurrence of COVID-19 is ≤ 30%, i.e.

H₀^{efficacy}: VE ≤ 0.3.

The first interim analysis was conducted based on a data snapshot occurred on 11-Nov-2020 whereas the data cut-off date for efficacy was 07-Nov-2020. At IA1, the median follow-up time was 49 days (7 weeks). The primary analysis of COVID-19 is based on the Per-Protocol (PP) set with cases starting 14 days after the 2nd dose. The IA1 efficacy analysis was performed by the independent biostatistician and the results were first reviewed by the independent external DSMB on 15-Nov-2020. The DSMB concluded that

“with 63% of the expected number of the total number of adjudicated primary endpoints, the study has passed the efficacy monitoring boundary for benefit.” The DSMB “encourages the study team to prepare the data for the FDA package as rapidly as possible.” Based on the DSMB’s recommendation, select Sponsor and CRO personnel were unblinded to prepare for regulatory submissions.

Vaccine efficacy of mRNA-1273 was demonstrated at IA1 based on the pre-specified success criterion on efficacy. As efficacy was demonstrated at IA1 based on 95 cases per adjudication committee, all subsequent efficacy analyses, if any, would be considered supportive or supplementary.

At IA1, the total number of COVID-19 starting 14 days after the 2nd injection based on the adjudication committee assessments (i.e. primary efficacy endpoint) was 95, 63% of the information fraction based on the total target number of 151. Correspondingly, the nominal one-sided alpha is 0.0047. At IA1, the one-sided p-value to test null hypothesis of VE \leq 30% from the stratified Cox proportional hazard model was <0.0001 , and was compared to the nominal one-sided alpha (0.0047) based on the number of cases at IA1 (95 in total). Equivalently, the lower-bound of the alpha-adjusted confidence interval of VE, the two-sided 99.1% CI, can be compared to 30% at IA1. The lower bound of the two-sided 99.1% CI was above 30% at IA1.

6.4.2.2. The Primary Analysis of Efficacy

To support regulatory submissions, in particular, to provide data with a median follow-up duration for safety and efficacy of at least two months after completion of the full vaccination regimen, a decision was made to perform a second analysis based on the data snapshot as of 25-Nov-2020 (DS2, whereas the data cut-off date for efficacy was 21-Nov-2020). Both safety and efficacy analyses were performed to provide additional information on the vaccine’s profile. As efficacy has been demonstrated at IA1, the analysis of efficacy based on the data snapshot of 25-Nov-2020 were supplementary in nature.

The date cutoff date for efficacy in the second analysis of efficacy was 21-Nov-2020. All potential COVID-19 cases starting 14 days after the 2nd injection confirmed by RT-PCR

(central or local), with corresponding minimal clinical data in electronic data capture (EDC) as of 21-Nov-2020 were sent to the Adjudication Committee. All these potential cases have been adjudicated for this analysis.

It was anticipated that the total number of COVID-19 cases based on the adjudication committee assessments starting 14 days after the 2nd injection in the Per-Protocol Set at DS2 on 25-Nov-2020 would be ≥ 151 , the target total number of events at the originally planned primary analysis. Therefore, this analysis was considered the primary analysis of efficacy of at least 151 cases, as prespecified in the protocol. At DS2, the total number of COVID-19 cases based on the adjudication committee assessments starting 14 days after the 2nd injection in the Per-Protocol Set was 196.

6.4.3. Final Analysis of Efficacy for blinded phase

Results from DS1 and DS2 were used to support EUA application in US and other regions of the world. EUA was authorized for mRNA-1273 in US on 18-December-2020.

The clinical study protocol (CSP) Amendment 6, dated 23-December-2020, informs all ongoing study participants of the availability of and eligibility criteria of any COVID-19 vaccine made available under an EUA and offers participants who originally received placebo in this study the potential benefit of vaccination against COVID-19, given that the primary efficacy endpoint for mRNA-1273 against COVID-19 was met per the protocol-defined interim analysis. Participants in this study will have a participant decision visit, at which participants would have the opportunity to be unblinded, and those originally randomized to placebo would have the opportunity to receive mRNA-1273 in this study.

A final efficacy analysis is planned to provide final efficacy update based on data from the blinded phase (Part A) of the study when approximately 90% of the study participants have had the participant decision visit or have been unblinded or discontinued from the study. At this final efficacy analysis of the blinded phase of the study, efficacy data up to the earlier of participant decision visit or unblinding visit, or data cutoff date for efficacy will be included in the analysis.

The analysis period of the blinded phase (Part A) for efficacy analyses will be used:

Part A Treatment Group	Description	Blinded/Part A Analysis Period for Efficacy
mRNA-1273	Participants randomized to mRNA-1273 in the Blinded Phase	From randomization to earlier date of (PDV/unblinding, study discontinuation, study completion, death, or data cutoff for efficacy)
Placebo	Participants randomized to Placebo in the Blinded Phase	From randomization to earlier date of (PDV/unblinding, study discontinuation, study completion, death, or data cutoff for efficacy)

At the time of the final analysis of efficacy for blinded phase date, summary of COVID-19 cases occurred during the open-label phase may be provided.

6.5. Multiplicity Adjustments

The overall type I error rate for this study is controlled at 2.5% (one-sided). The overall Type I error rate for the primary efficacy endpoint at the IAs and the primary analysis is strictly controlled at 2.5% (1-sided) based on the Lan-DeMets O'Brien-Fleming approximation spending function. The primary efficacy endpoint will be considered statistically significant after consideration of the strategy for controlling the Type I error as described in Section 6.4 Interim Analyses. Statistical significance of the primary efficacy endpoint can be achieved at either one of the interim analyses or at the primary analysis. A sequential/hierarchical testing procedure will be used to control type 1 error rate over the primary efficacy endpoint and the secondary efficacy endpoints. Secondary efficacy endpoints will only be tested when the primary efficacy endpoint achieves statistical significance.

If the primary efficacy endpoint achieves statistical significance at either one of the interim analyses or at the primary analysis, a fixed-sequence statistical strategy will be used to test the following secondary efficacy endpoints in a pre-defined order:

1. secondary efficacy endpoint: COVID-19 regardless of evidence of prior SARS -CoV-2 infection at the same analysis (through the same follow-up period)

2. secondary efficacy endpoint: infection regardless of symptomatology or severity at the same analysis (through the same follow-up period)
3. secondary efficacy endpoint: severe COVID-19 at the analysis with ≥ 20 cases, otherwise, to test at the end of the study

[figure not shown]
If the primary efficacy endpoint achieves statistical significance at either one of the interim analyses or at the primary analysis, sequential tests of the above 3 secondary efficacy endpoints will be performed at one-sided Type I error rate of 0.025.

All hypothesis tests against the above three secondary efficacy endpoints will be first against a $VE \leq 0\%$ null hypothesis. If hypothesis test against $VE \leq 0\%$ are rejected for all three, sequential testing against a $VE \leq 10\%$ for these three secondary efficacy endpoints will be performed in the same order; if hypothesis test against $VE \leq 10\%$ are rejected for all three, sequential testing against a $VE \leq 20\%$ for these three secondary efficacy endpoints will be performed in the same order; if hypothesis test against $VE \leq 20\%$ are rejected for all three, sequential testing against a $VE \leq 30\%$ for these three secondary efficacy endpoints will be performed in the same order. No further testing will be performed once the sequence breaks, that is, further testing stops as soon as an endpoint in the sequence fails to show significance against corresponding null hypothesis.

No further testing will be performed once the sequence breaks, that is, further testing stops as soon as an endpoint in the sequence fails to show significance against corresponding null hypothesis regarding VE.

While achieving vaccine efficacy that rules out a lower bound of 30% against COVID-19 is the goal of the study, there is utility in formally assessing VEs that are less than 30%. Therefore, in the situation that the primary efficacy endpoint (VE against COVID-19) does not achieve statistical significance against a $VE \leq 30\%$ null hypothesis at neither the interim analyses nor the primary analysis, at the primary analysis, sequential testing against a $VE \leq 20\%$, a $VE \leq 10\%$, and a $VE \leq 0\%$ will be performed, halting when a rejection occurs. Figure 2 below demonstrates the testing strategy in this study:

Figure 2: Testing Strategy of Primary and Secondary Efficacy Endpoints

At the first interim analysis where vaccine efficacy for COVID-19 has been demonstrated at the pre-specified statistical criterion, there were 11 total severe COVID-19 cases based on adjudication committee starting 14 days after the 2nd injection.

At the time of IA1 and the primary analysis of efficacy, data for secondary efficacy endpoint infection regardless of symptomatology or severity were not available and were not included in these analyses.

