9.5. Statistical Analyses

This section provides a summary of the planned statistical analyses of the primary and secondary endpoints.

The overall Type I error rate for the primary endpoint at the IAs and the primary analysis is strictly controlled at 2.5% (1-sided) based on the Lan-DeMets O'Brien-Fleming approximation spending function (see [Section 9.6](#) for details). The primary efficacy results that will be considered statistically significant after consideration of the strategy for controlling the Type I error as described in [Section 9.6](#). Statistical significance of the primary efficacy endpoint can be achieved at either one of the IAs or at the primary analysis. A sequential/hierarchical testing procedure will be used to control Type 1 error rate over the primary efficacy endpoint and the secondary efficacy endpoints. Secondary efficacy endpoints will only be tested when the primary efficacy endpoint achieves statistical significance. Multiplicity adjustments among the secondary efficacy endpoints may be performed for secondary efficacy endpoints, in that case, will be specified in the SAP.

No formal multiple comparison adjustments will be employed for multiple safety endpoints or multiple efficacy endpoints. Nominal p-values and CIs may be computed for other efficacy analyses without controlling for multiplicity as a measure of VE.

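### The stated 2.5% overall error control does not strictly hold for the first two secondary endpoints, which are tested at a flat 0.025 at whichever look the primary crosses

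*SAP*

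**What the plan says.** SAP (Part A) section 6.5 opens with "The overall type I error rate for this study is controlled at 2.5% (one-sided"). It then gives the primary endpoint Lan-DeMets O'Brien-Fleming spending over the two interims and the primary analysis. Section 6.4.1 sets the interims at "35% and 70% of the target total number of COVID-19 cases across the two vaccine groups" and lists nominal one-sided levels of 0.0002, 0.0073 and 0.0227 at 53, 106 and 151 cases.

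For the secondaries, "a fixed-sequence statistical strategy will be used to test the following secondary efficacy endpoints in a pre-defined order", and "sequential tests of the above 3 secondary efficacy endpoints will be performed at one-sided Type I error rate of 0.025". Timing differs by endpoint:

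- First, COVID-19 regardless of prior infection: the look at which the primary succeeds.
- Second: "infection regardless of symptomatology or severity at the same analysis (through the same follow-up period").
- Third: "severe COVID-19 at the analysis with ≥ 20 cases, otherwise, to test at the end of the study".

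"All hypothesis tests against the above three secondary efficacy endpoints will be first against a" VE ≤ 0% null. The 10%, 20% and 30% nulls follow only if all three endpoints pass the step before. No interim boundary is given for any secondary.

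Protocol section 9.5 makes the general commitment ("A sequential/hierarchical testing procedure will be used to control Type 1 error rate over the primary efficacy endpoint and the secondary efficacy endpoints") and leaves adjustment among the secondaries to the SAP.

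**The concern.** A fixed sequence deals with having several endpoints. It does not deal with a test date that depends on the data. A high primary statistic selects an early look, and a secondary that shares events with the primary tends to be high at that same look, where it receives the full 0.025. Testing each secondary only once does not remove the problem, because the choice of when to test is informative.

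The sharing follows from the plan. SAP section 4.3 notes that every COVID-19 case is also an infection case. Section 6.3.2.2 analyses COVID-19 regardless of prior infection with the primary's methods in the larger Full Analysis Set. What is at stake is the accuracy of an unqualified statement of family-wise control, on which formal secondary claims rest.

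**Working it through.** **1. Reproduce the primary design.** The spending function is α*(t) = 2[1 − Φ(z₀.₉₈₇₅/√t)] with z₀.₉₈₇₅ = 2.241.

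- At t = 0.35: 2.241/0.592 = 3.79, so α* = 0.00015, which rounds to the stated 0.0002.
- Solving for the later looks gives nominal 0.0073 and 0.0227, as stated.
- At t = 95/151 = 0.629: 2.241/0.793 = 2.83, so α* = 0.0047, as in SAP section 6.4.2.1.
- Events for HR 0.4 against 0.7: variances 1/[(0.7/1.7)(1/1.7)] = 4.13 under the null and 1/[(0.4/1.4)(1/1.4)] = 4.90 under the alternative. Then (1.96√4.13 + 1.282√4.90)² / (ln 0.4/0.7)² = 148.5. Times the group-sequential factor 1.014 this is 150.6, so 151 as stated.
- The drift giving 90% power is about 3.26.

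**2. Correlation (assumption).** The documents give none. For nested events, the correlation of the two log-rank statistics is about √(share of secondary events that are also primary events). If 30% of infections were primary cases, it would be √0.30 = 0.55.

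**3. Error of one true-null secondary.** At look k with information fraction t, the primary statistic Z has mean δ√t and the secondary statistic S has mean 0, with correlation ρ. Equal information fractions are assumed for the two endpoints. The error is

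Σₖ P(Zⱼ < bⱼ for all j < k, Zₖ ≥ bₖ, Sₖ ≥ 1.96).

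Simulation with 3 million paths gives:

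| Setting | ρ = 0.5 | ρ = 0.55 |
|---|---|---|
| Looks 53/106/151, maximum over the primary effect | 2.9% | 2.9% |
| Looks 53/106/151, planning effect VE 60% | 2.8% | 2.9% |
| Looks 95/151, maximum over the primary effect | 2.7% | 2.7% |
| Tested once at full information after any primary crossing | 2.5% | 2.5% |

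At VE 60%, ρ = 0.55 and the planned looks, the three looks contribute 0.80% + 1.91% + 0.16% = 2.9%. The first look is reached as the crossing look in only 4.7% of trials, yet it supplies more than a quarter of the error. At ρ = 0 the error does not exceed 2.5%.

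**4. Higher correlations.** The planned-look maximum rises to 3.5% at ρ = 0.89 and 4.1% at ρ = 1.0. These need a true-null secondary beside an effective primary. If a share s of placebo-arm secondary events are primary cases with hazard ratio h, a secondary VE of exactly 0% needs a hazard ratio of (1 − s·h)/(1 − s) in the remaining events.

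- s = 0.9, h = 0.5: (1 − 0.45)/0.1 = 5.5, which is implausible.
- s = 0.3, h = 0.4: (1 − 0.12)/0.7 = 1.26. This is conceivable, for example if the vaccine turned symptomatic infections into asymptomatic ones.

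**5. After the change.** A secondary tested against its own spending boundary keeps its error at or below 2.5% for any correlation by construction. The largest value found with O'Brien-Fleming-type levels was 1.6%.

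**The case against.** The strongest reply is that little of this applied in the trial as run. SAP section 6.5 records that infection data were not available at the first interim or the primary analysis, and that there were 11 severe cases at the first interim, below the 20 required. The second endpoint in the sequence was therefore missing. On the stated order, only the VE ≤ 0% test for COVID-19 regardless of prior infection could be reached at that look. That endpoint overlaps heavily with the primary, so a true null beside an effective primary is close to impossible. At the VE of 94.5% reported in the SAP for Parts B and C (drift about 6.9), crossing at 95 cases is almost certain and the error returns to about 2.5%.

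All of this stands, and it limits the reach of the point. It does not make the sentence in section 6.5 correct, because control claimed without qualification has to hold for any true null. Version 2.0 of the SAP kept the same-look rule and the flat 0.025 after recording these facts, and it does not say where infection will be formally tested.

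A reader might infer more: that all three secondaries are affected, that the error is near 4%, that infection carries most of the excess, or that the primary result is in doubt. The documents do not support these readings. Severe COVID-19 has its own case-count trigger. The 4% figure needs a correlation of 1. Infection was not tested at the look where the primary crossed. The primary's own 2.5% control is intact.

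**Conclusion.** The point holds in limited form. As planned, the first two secondaries have a one-sided error of about 2.9% at correlation 0.5 to 0.55, against the stated 2.5%. With looks at 95 and 151 cases, the error is at most about 2.7% at correlation 0.5. As conducted, the mechanism applies mainly to COVID-19 regardless of prior infection. An infection endpoint tested once, at a later analysis whose timing does not depend on the primary statistic, shows no inflation.

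These sizes rest on an assumed correlation, on equal information fractions for primary and secondary, and on a secondary that is truly null. The excess is small, and nothing here shows that any secondary result is a false positive. The statement of overall control is nevertheless wrong as written.

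**What to change.** In SAP (Part A) section 6.5:

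- For any secondary tested at an interim look, replace the flat 0.025 with that endpoint's own spending level at that look, for example the O'Brien-Fleming-type 0.0047 at 95 of 151 cases. Name the information fraction used, since the documents set no target event total for these endpoints.
- State that infection regardless of symptoms is formally tested once, at a fixed later analysis such as the final blinded analysis of section 6.4.3. Its trigger is participant status, not a primary boundary, so 0.025 is valid there.

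The primary crossed before version 2.0 was written, so boundaries set now for that look would be post hoc. If they are not adopted, restrict the 2.5% control statement to the primary endpoint and label interim secondary p-values as nominal.

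The cost is stricter interim thresholds for the secondaries, or a weaker stated claim. No new data are needed.

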6.6. Safety Analysis

Safety and reactogenicity will be assessed by clinical review of all relevant parameters including solicited ARs (local and systemic), unsolicited AEs, SAEs, MAAEs, AEs leading to withdrawal from study vaccine and/or study participation, vital signs, and physical examination findings. Solicited ARs and unsolicited AEs will be coded by SOC and PT according to the MedDRA. The Toxicity Grading Scale for Healthy Adult and Adolescent Volunteers Enrolled in Preventative Vaccine Clinical Trials ([DHHS 2007](#)) is used in this study with modifications for solicited ARs as presented in Table 4 of the study protocol.

All safety analyses will be based on the Safety Set, except summaries of solicited ARs which will be based on the Solicited Safety Set. All safety analyses will be provided by treatment group, unless otherwise specified. Unless specified otherwise, the language in this section pertains to Part A.

